7.1. Study Design

This non-interventional cohort study will enroll adult PwSHA treated in routine clinical practice with either Roctavian or SoC hemostatic prophylaxis treatment with exogenous FVIII replacement therapies or emicizumab in Germany. Study participants will be followed based on data prospectively entered into the German Hemophilia Register (i.e., Deutsches Hämophilieregister [DHR]). All participants are expected to have previously enrolled in the DHR per local regulations. Study participants will consent for their data that is collected in the DHR to be utilized for this study, consistent with the requirements of the AbD. Participants will provide consent during a study recruitment period beginning approximately 3 months after this protocol is agreed with the G-BA (to allow for ethics committee approval of the final protocol) and ending approximately 42 months prior to the date of the final report required by the G-BA resolution for the AbD. This study recruitment period window will allow for 3 years of follow-up for each participant in the DHR prior to the data cut required to report on the study for the purposes of the AbD.

Participants will be assigned to a study cohort based on the treatment that was received during the recruitment period. On and/or before the start of the study recruitment period, participants would have received SoC treatments, thus this study is centered around a prevalent new user design.¹⁰ All participants receiving Roctavian during the recruitment period will be assigned to the Roctavian Cohort. Participants receiving SoC hemostatic prophylaxis treatment only during the recruitment period will be assigned to the SoC Cohort. Index date will be defined as the date of Roctavian administration for PwSHA treated with Roctavian (Roctavian Cohort) and the date of consent for PwSHA treated with SoC products (SoC Cohort). Participants will be followed for 3 years after index date (follow-up period) based on data extracted from the DHR. If a participant consents to the AbD while on SoC and subsequently receives Roctavian during the recruitment period, inclusion/exclusion criteria will be reassessed at the time of Roctavian administration. For these participants, baseline assessments, including patient reported outcome measures, will also be re-assessed at the time of Roctavian administration. If a participant in the SoC Cohort subsequently receives Roctavian during follow-up after the recruitment period, their data will be censored for analysis. Study participants will be followed consistent with the Study Elements of Interest (see Study Protocol and Section 7.4) from index through the follow-up period. The study aims to enroll at least 70 PwSHA into the Roctavian Cohort and at least 330 PwSHA into the SoC Cohort. The study is anticipated to be completed approximately 6 months prior to the final report required to be submitted to the G-BA. Figure 1 illustrates the overall study conduct. The study completion date is based on allowing time to analyze data and submit a final report on the AbD defined by the G-BA resolution. Changes to the AbD defined deadlines for the final report would result in changes to the study completion timeframe, as well as the recruitment window described above.

[figure not shown]

Figure 1: Study Schema

The Roctavian and SoC Cohorts will be compared based on events observed during the follow-up period regarding bleeding events, use of hemostatic medication, clinical outcome assessments measuring joint health, quality of life, pain, and safety (all cause death, hemophilia-related death, adverse events (AEs) leading to hospitalization and death, and targeted AEs of FVIII inhibitor development, thrombotic events, new malignancies, and severe liver disease). PwSHA in Germany are generally seen at a hemophilia treatment center (HTC) every 6 months and therefore it is expected that clinical outcome assessments of quality of life and pain would be assessed at those timepoints, with joint health assessed at least annually.

Comparisons of safety will also be conducted. The occurrence of and time to resumption of prophylactic hemostatic therapy will also be described among the Roctavian Cohort during the follow-up period. The Roctavian and SoC Cohorts will be compared after propensity score adjustment for differences in baseline characteristics (e.g., demographic and clinical variables recorded in the DHR prior to the index date). These characteristics will also be used to describe the Cohorts and to inform the propensity score. Potential variables to be included in the propensity score, based on association with the primary outcome, were identified from the literature and discussion with German clinicians. Exact variables included in the propensity score will be based on statistical, as well as clinical associations, between baseline characteristics and the likelihood of receiving Roctavian therapy.

7.2. Study Estimand

7.2.1. Treatment Policy vs. Hypothetical Estimands

Due to the non-randomized, non-interventional nature of this study, two estimands will be considered when estimating the comparative effectiveness of Roctavian to SoC - the treatment policy estimand and the hypothetical estimand. The treatment policy estimand ignores intercurrent events (not applying censoring or any missing data analysis), while the hypothetical estimand may use censoring or missing data analysis methods to derive an estimate incorporating the effect of an intercurrent event like treatment switching. The treatment policy estimand can be overly conservative if switching occurs between the treatment arms in an analysis, while the hypothetical estimand is targeting to adjust for this effect.

Due to the study design, along with the management and administration of Roctavian therapy, the treatment policy (similar to intent to treat analysis) is likely be overly conservative in the setting of this study and the hypothetical estimand is expected to provide more clinically interpretable results. In particular, after the administration of Roctavian, PwSHA will continue their SoC prophylaxis therapy in the initial weeks after infusion and therefore have a period where bleeding events and hemostatic treatment utilization are not reflective of the treatment effect of only Roctavian. Additionally, participants in the Roctavian Cohort may return to prophylaxis, and due to the non-interventional

design PwSHA in the SoC Cohort may switch to Roctavian after the study recruitment window. Further, the hypothetical estimand is consistent with the analyses described in the summary of product characteristics (SmPC)¹¹ and would allow for consistency of interpretation between this study and data described in the SmPC. Although the study sponsor's position is that the hypothetical estimand will provide more clinically interpretable results, the G-BA resolution dated 21, Sept 2023¹² required the conduct of analyses based on the treatment policy estimand. Therefore, analyses will be conducted and reported utilizing both estimands. Consistency in results for the different estimands and impact on the interpretation of results will be discussed in the interim and final reports.

7.2.2. Treatment Policy Estimand

Analyses based on the treatment policy estimand will describe outcomes from index through the end of the follow-up period for both the Roctavian Cohort and SoC Cohort. A participants' time in the analysis will only be censored in the event of a withdrawal, loss to follow-up, death or enrollment in an interventional trial. Follow-up will be censored based the earliest date after index of withdrawal, loss to follow-up, enrollment into an interventional clinical trial, death (inclusive of date of death), end of reporting/follow-up period in the DHR, or end of study follow-up (e.g., index date +3 years). Due to the non-interventional nature of the study and AbD, a participant in the SoC Cohort may subsequently receive Roctavian during follow-up after the recruitment period, if this occurs this participant will be excluded from the analysis. If a participant in the Roctavian Cohort returns to prophylaxis with another hemostatic therapy (e.g., exogenous FVIII or emicizumab), this participant will be maintained in the analysis (i.e., not excluded from the analysis) as there is a potential continued benefit of the gene therapy after prophylaxis is resumed for effectiveness outcomes and potential long term risk of safety events associated with Roctavian therapy.

Outcomes for participants in the SoC Cohort who are treated with Roctavian during follow-up after the recruitment period, and are excluded from the analysis, will be described separately. Outcomes will be described for the period these participants were on SoC (index to date to Roctavian infusion) and treated with Roctavian (date of Roctavian infusion through the end of follow-up).

Figure 2 below illustrates the treatment policy estimand analysis.

[figure not shown]

Figure 2: Treatment Policy Estimand Study Schema

Figure note: Outcomes described from index through the end of the follow-up period for both the Roctavian Cohort and SoC Cohort. A participants' time in the analysis will only be censored in the event of a withdrawal, loss to follow-up, death or enrollment in an interventional trial (based on earliest date of). Any participant in the SoC Cohort who subsequently receives Roctavian during follow-up after the recruitment period will be excluded from the analysis.

7.2.3. Hypothetical Estimand

Analyses based on the hypothetical estimand will describe outcomes during the follow-up period for both the Roctavian Cohort and SoC Cohort, minimizing time periods during which outcomes are confounded by exposure to both Roctavian gene therapy and SoC prophylaxis. As PwSHA administered Roctavian will remain on prophylaxis for a time following the index date as endogenous FVIII production initiates, the analytical follow-up period for outcomes such as bleeding events and hemostatic therapy utilization for the Roctavian Cohort will begin on 5 weeks post-infusion or 3 days after the end of routine FVIII prophylaxis (whichever occurs later), or 27 weeks after end of emicizumab prophylaxis consistent with analyses of the Roctavian clinical trials.¹³ The analytical follow-up period of the SoC Cohort will begin on the index date. Participants in the Roctavian Cohort will be censored at the time of resumption of SoC prophylaxis and participants in the SoC Cohort who subsequently receive Roctavian during follow-up after the recruitment period, will be censored on the date of Roctavian infusion. As with the treatment policy estimand, for both Cohorts a participants' time in the analysis will be censored in the event of a withdrawal, loss to follow-up, death or enrollment in an interventional trial. Follow-up will be censored based on the earliest date after index of any of the censoring events described above. Figure 3 below illustrates the hypothetical estimand analysis.

[figure not shown]

Figure 3: Hypothetical Estimand Study Schema

Figure note: For the Roctavian Cohort, analytical follow-up period for outcomes such as bleeding events and hemostatic therapy utilization will begin on 5 weeks post-infusion or 3 days after the end of routine FVIII prophylaxis (whichever occurs later), or 27 weeks after end of emicizumab prophylaxis consistent with analyses of the Roctavian clinical trials. Participants in the Roctavian Cohort will be censored at the time of resumption of SoC prophylaxis. For the SoC Cohort, analytical follow-up period of the SoC Cohort will begin on the index date. Participants in the SoC Cohort who subsequently receive Roctavian during follow-up after the recruitment period, will be censored on the date of Roctavian infusion.

7.3. Setting

7.3.1. Study Time Period

The study period from the start of data collection accompanying the application to approximately 6 months prior to the date of the final report required by the G-BA resolution for AbD represents the entirety of the dataset. Participants will provide consent during a study recruitment period as outlined in Section 7.1. The 12 months immediately prior to their index date will be utilized for baseline description of clinical variables such as bleeding events and hemostatic medication utilization. It is anticipated that participants will have 12 months baseline data in the DHR prior to the index date, though this is not mandatory. Participants will be followed in the Cohorts for a maximum of three years from their index date.

The study completion date is based on allowing time to analyze data and submit a report per the AbD deadline. Changes to the AbD defined deadlines for the report would result in changes to the study completion timeframe, as well as the recruitment window described above.

7.3.2. Index Date

For participants in the Roctavian Cohort, the index date will be the date of Roctavian administration during the recruitment period. For participants in the SoC Cohort, the index date will be the date of participant consent into the study during the same recruitment period.

7.3.3. Follow-up Period and Censoring

Participants will be followed for three years post-index date.

7.3.3.1. Censoring Criteria due to Withdrawal and/or Death

Participants will be censored from the study due to any of the following reasons:

- Participant or their legally authorized representative withdraws their consent to participate in the study
- Death
- Lost to follow-up (repeatedly fails to attend visits or respond to attempts at contact)
- Use of any investigational product or investigational medical device during the study period
- Participant was erroneously admitted into the study or does not meet inclusion/exclusion criteria
- Participant no longer has severe HA (e.g., subject has received liver transplant)
- For SoC Cohort, if a participant is administered Roctavian after study consent

Follow-up time will end at the point at which any of the above events occur. For participants who withdraw from the study and/or initiate participation in a clinical trial, physicians are expected to enter data for the variables 'Data entered as observed after index' or 'End of Follow-up' with the data censored in the analysis at the date of withdrawal/trial initiation/gene therapy administration.

If participants are censored from the study while the recruitment window is ongoing, new participants may be selected for replacement.

7.3.3.2. Censoring and Follow-up Criteria due to Hypothetical Estimand

Analytical Considerations

For the analysis under the hypothetical estimand, the following additional censoring criteria will be applied:

- Treatment switching from SoC to Roctavian (or vice versa) anytime during the study period
- Analytical follow-up time after Roctavian administration before 5 weeks post-infusion or 3 days before the end of routine FVIII prophylaxis (whichever occurs later), or 27 weeks before end of emicizumab prophylaxis (for outcomes such as bleeding events and hemostatic therapy utilization)

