Death			X ^g	At participant discontinuation ^g
Hemophilia-related death			X ^g	At participant discontinuation ^g
Adverse events leading to hospitalization ^h or death			X ^g	At end of study period or participant discontinuation ^g
Thromboembolic events			X ^g	At end of study period or participant discontinuation ^g
Severe liver disease (liver failure, liver fibrosis and/or progression of liver fibrosis or cirrhosis)			X ^g	At end of study period or participant discontinuation ^g
New malignant neoplasms			X ^g	At end of study period or participant discontinuation ^g

AAV, Adeno-associated virus; BPI-SF, Brief Pain Inventory-Short Form; FVIII, factor VIII; HJHS, Hemophilia Joint Health Score, QoL-A, quality of life assessment; SoC, standard of care.

a Based on data recorded in the DHR for the 12 months prior to index (or portion thereof)

b Recorded for the Roctavian Cohort only

c Assessment requested to be completed for all AbD participants on index or the 60 days prior to index and entered into the DHR consistent with routine clinical management of a participant.

d Assessment requested to be completed for all AbD participants entered into the DHR approximately every 6 months relative to the index date during follow-up consistent with routine clinical management of a participant.

e Assessment requested to be completed for all AbD participants entered into the DHR at least every year relative to the index date during follow-up consistent with routine clinical management of a participant.

f Assessment requested to be completed for all AbD participants entered into the DHR at end of follow-up (approximately 3 years after the index date) consistent with routine clinical management of a participant or at the time of discontinuation.

g Data requested to be entered through the study period including at the end of the study period (approximately 3 years after the index date) or at time of participant discontinuation.

h Hospitalization defined as a participant having been admitted to the hospital for inpatient care, either to the inpatient ward or to the emergency room for observation and/or treatment that would not have been appropriate in the physician’s office or outpatient setting.

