10.3.2.3. Hypothetical Estimand

Analyses based on the hypothetical estimand will describe outcomes during the follow-up period for both the Roctavian Cohort and SoC Cohort, minimizing time periods during which outcomes are confounded by exposure to both gene therapy and SoC prophylaxis. As PwSHA administered Roctavian will remain on prophylaxis for a time following the index date as endogenous FVIII production initiates, the analytical follow-up period for outcomes such as bleeding events and hemostatic therapy utilization for the Roctavian Cohort will begin 5 weeks post-infusion or 3 days after the end of routine FVIII prophylaxis (whichever occurs later), or 27 weeks after end of emicizumab prophylaxis consistent with analyses of the Roctavian clinical trials. The analytical follow-up period of the SoC Cohort will begin on the index date. Participants in the Roctavian Cohort will be censored at the time of resumption of SoC prophylaxis and participants in the SoC Cohort who subsequently receive Roctavian during follow-up after the recruitment period, will be censored on the date of Roctavian infusion. As with the treatment policy estimand, for both cohorts a participant’s time in the analysis will be censored in the event of a withdrawal, loss to follow-up, death or

enrollment in an interventional trial. Follow-up will be censored based the earliest date after index of any of the censoring events described above.

Figure 3 below illustrates the hypothetical estimand analysis.

Figure 3: Analysis Schema for Hypothetical Estimand

[figure not shown]

Figure note: For the Roctavian Cohort, analytical follow-up period for outcomes such as bleeding events and hemostatic therapy utilization will begin on 5 weeks post-infusion or 3 days after the end of routine FVIII prophylaxis (whichever occurs later), or 27 weeks after end of emicizumab prophylaxis consistent with analyses of the Roctavian clinical trials. Participants in the Roctavian Cohort will be censored at the time of resumption of SoC prophylaxis. For the SoC Cohort, analytical follow-up period of the SoC Cohort will begin on the index date. Participants in the SoC Cohort who subsequently receive Roctavian during follow-up after the recruitment period, will be censored on the date of Roctavian infusion.

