7.4.1. Baseline Variables

Table 3 includes study variables that will be captured to describe the Roctavian and SoC Cohorts based on data collected on or before their index date, or to be entered at the index date reflecting annual reporting into the DHR for the time period prior to the index date. Measures will be assessed at the most recent time point prior to the index date, unless otherwise specified.

Table 3: Baseline Variables

Variable	Captured in DHR	DHR data field name(s)	Operational definition/description
Unique participant ID	Yes (Derived)	Unique identifier for participants at an HTC are utilized in the DHR. Outputs from the DHR are anonymized, though a consistent study center code and de-identified participant id at that site will be available to identify participants	
 Calculated field based on a de-identified study center code and unique participant code (e.g., participant at study center A may be identified as A-101)
Index date	Yes	
 Patient takes part in data collection during the application? Start of the AbD (date of consent) 	
 ddmmyyy Date of Roctavian administration for Roctavian Cohort Date of study consent for SoC Cohort
Age	Yes (calculated)	
 Year of birth¹ 	
 Age at Index Date (continuous) Age groups: 18-40, 41-64, 65+ Age groups in 5-year increments
Age at HA diagnosis	Yes (calculated)	
 Year of birth¹ Date of diagnosis 	
 Age at HA diagnosis derived from participant’s year of birth and date of diagnosis, unless date of diagnosis is recorded as “unknown” Reported similar to the Age variable above
Age at first FVIII therapy administration	Yes (calculated)	
 Year of birth¹ Date of the first factor administration 	
 Age at first FVIII therapy administration derived from participant’s year of birth and date of first FVIII administration, unless date of administration is recorded as “unknown”

Variable	Captured in DHR	DHR data field name(s)	Operational definition/description
HTC	--		
 Derived from the site associated with study consent and primarily managing a participant De-identified form based on HTC identifier collected in DHR

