7.9.4.4. Clinical Outcome Assessments

Population	Measurement Period	Analysis Notes
All participants with sufficient follow-up, comparing Roctavian Cohort to SoC Cohort; Participants without any COA scores will not be included	Assessments are expected to be conducted at baseline and every 6 months for quality of life and pain, and for joint health at least annually	For analyses of change from baseline, participants are expected to have baseline and at least one follow-up measure

The Hemophilia Joint Health Score (HJHS), Haemo-QoL-A, and Brief Pain Inventory – short form (BPI-sf) will be used as COAs. As these instruments standardize collection of data for areas that are monitored in routine clinical practice, the assessments are expected to follow routine clinical follow-up. Physicians participating in the AbD are expected to enter data for these instruments collected relative to the study index date per the operational definitions outlined in Table 5. The following Table 8 includes the assessment timepoints of interest throughout the follow-up and tolerance windows. If a participant has multiple measurements reported in the same window, the measurement closest to the time point of interest will be selected. An individual data point will only be utilized once in the analysis (e.g., if there is a measure at 1.2 years, this data point would only be used for 1 year and not the 2 year analysis).

Table 8. COA Timepoints of Interest and Tolerance Windows

Timepoints of Interest	Day of Assessment	Tolerance Window ¹
Baseline	Index date, day 0	0-91 days
6-months	Day 182	92-273 days
12-months (1 year)	Day 365	274-456 days
18-months	Day 547	457-638 days
24-months (2 years)	Day 730	639-821 days
30-months	Day 912	822-1,003 days
36-months (3 years)	Day 1,095	1,004-1,185 days

1. Tolerance windows are +/- 3 months before and after the expected assessment day.

Note: HJHS assessments will be completely annually, while Haemo-QoL-A and BPI-sf assessments will be completed every 6 months.

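### The SAP reverses the start rule for Roctavian follow-up under the hypothetical estimand, and prints a baseline window for the clinical outcome assessments that runs after index

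*Protocol*

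**What the plan says.** **Start of Roctavian follow-up, hypothetical estimand.** Protocol 10.3.2.3 begins the analytical follow-up for outcomes such as bleeding and hemostatic use at "5 weeks post-infusion or 3 days after the end of routine FVIII prophylaxis (whichever occurs later), or 27 weeks after end of emicizumab prophylaxis". Its stated purpose is "minimizing time periods during which outcomes are confounded by exposure to both gene therapy and SoC prophylaxis". SAP 7.2.3 repeats the rule: "3 days after the end of routine FVIII prophylaxis (whichever occurs later), or 27 weeks after end of emicizumab prophylaxis". SAP 7.3.3.2, which lists the additional censoring criteria for this estimand, keeps the 5-week point but then excludes time only up to "3 days before the end of routine FVIII prophylaxis (whichever occurs later), or 27 weeks before end of emicizumab prophylaxis".

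**Baseline for HJHS, Haemo-QoL-A and BPI-SF.** Footnote c of protocol Table 2 reads "Assessment requested to be completed for all AbD participants on index or the 60 days prior to index". SAP 7.4.1 says of baseline variables "Measures will be assessed at the most recent time point prior to the index date, unless otherwise specified", and SAP 7.9.2 takes baseline characteristics from before the index date. SAP Table 8 (section 7.9.4.4) places the baseline assessment at day 0 with a window of 0 to 91 days. The 6-month window follows at days 92 to 273. The footnote to the same table says "Tolerance windows are +/- 3 months before and after the expected assessment day".

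**The concern.** Both passages fix which observations enter a comparison, and each conflicts with another part of the plan.

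In the first, the direction is reversed for both drug classes. A programmer who follows the list of censoring criteria would open Roctavian follow-up while prophylaxis, or its washout, is still acting. That is the period the hypothetical estimand is meant to keep out. The rule governs analysable time for the primary outcome under the estimand that the sponsor regards as more clinically interpretable. For bleeding rates, covered time would tend to favour Roctavian. For hemostatic use, counting the remaining prophylaxis doses would work against it. In either case the result is not the declared estimand.

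In the second, a score taken after infusion can stand as a Roctavian participant's baseline. Change from baseline and the 15% responder analyses are measured from that value, and the mixed models use it as their first time point. The change analyses require an evaluable baseline, so a window that leaves out the scores the protocol asks for would also remove participants.

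**Working it through.** The plan gives no calculated figure that depends on these windows, and the sample size does not enter. The check is date arithmetic. Let E be the end of prophylaxis counted from infusion. The documents do not give E, so a range is shown as an assumption.

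**FVIII users (days).** Rule in SAP 7.2.3 and protocol 10.3.2.3: start = max(35, E + 3). Rule as printed in SAP 7.3.3.2: start = max(35, E - 3).

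| E | 7.2.3 start | 7.3.3.2 start | Difference |
|---|---|---|---|
| 28 | 35 | 35 | 0 |
| 32 | 35 | 35 | 0 |
| 35 | 38 | 35 | 3 |
| 36 | 39 | 35 | 4 |
| 38 | 41 | 35 | 6 |
| 84 | 87 | 81 | 6 |

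The difference is 0 up to E = 32, 1 to 5 days for E = 33 to 37, and 6 days from E = 38. The printed rule opens before prophylaxis has ended only when E is beyond day 35, and then by at most 3 days.

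**Emicizumab users (weeks).** Rule in 7.2.3: start = E + 27. Rule as printed in 7.3.3.2: start = E - 27. The nominal gap is 27 + 27 = 54 weeks, or 378 days; 378/1,096 = 34% of a 3-year follow-up. Follow-up cannot open before infusion, so the printed start is bounded at week 0, or at week 5 if the 5-week point also applies to emicizumab users, which the sentence leaves unclear.

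| E | 7.2.3 start | 7.3.3.2 start (no floor / week-5 floor) | Extra weeks counted |
|---|---|---|---|
| 0 | 27 | 0 / 5 | 27 / 22 |
| 4 | 31 | 0 / 5 | 31 / 26 |
| 8 | 35 | 0 / 5 | 35 / 30 |
| 12 | 39 | 0 / 5 | 39 / 34 |
| 26 | 53 | 0 / 5 | 53 / 48 |

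Over E = 0 to 26 the excess is therefore 22 to 53 weeks per emicizumab user. Of these, 27 weeks (22 when E = 0 and the floor applies, 26 when E = 4 and it applies) lie after emicizumab has ended and are washout. The rest are weeks still on the drug.

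**Baseline window (days from index).**

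| Source | Window |
|---|---|
| Protocol Table 2, footnote c | -60 to 0 |
| SAP 7.4.1 and 7.9.2 | before index (7.4.1 also allows index) |
| SAP Table 8 as printed | 0 to 91 |
| SAP Table 8 footnote applied to day 0 | about -91 to +91 |

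The printed window counts forward from index, because the next row starts at day 92. It shares only day 0 with the protocol window, so a score from days -60 to -1, taken as the protocol asks, falls outside it. The footnote reading brings those scores back, but it still admits scores up to day 91 and still differs from 60 days.

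**The case against.** The reversal in 7.3.3.2 may well be a drafting slip. The text and figure notes of SAP 7.2.3 and protocol 10.3.2.3 all say the opposite, and protocol 10.3 calls the SAP a draft to be finalized before the first data cut. That is a fair account of how it arose. But the SAP has no rule for which section governs, and SAP 7.9.3 adds another start, the index date for both cohorts, without separating the estimands.

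A reader might infer that Roctavian follow-up generally opens well before prophylaxis has ended. The documents do not support that. For FVIII the effect is a matter of days. If emicizumab ends at infusion, the extra 22 to 27 weeks are all washout. The treatment policy estimand, which the G-BA required, counts from index and is untouched.

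On baseline, a reader might infer that every pre-index score is lost. That holds only on the printed window, since the table's own footnote can be read as keeping them. SAP 7.9.4.4 also takes the measurement closest to the timepoint, so an index-day score displaces any later one. What stands is that post-index scores are admitted when nothing closer exists.

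Nor do the documents support treating week 5 as the onset of effect on these instruments. That point is defined for outcomes such as bleeding and hemostatic use, and no passage dates an effect on joint health, quality of life or pain. Finally, a post-infusion baseline can arise only in the Roctavian Cohort, and these outcomes are secondary with nominal p-values.

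**Conclusion.** Both contradictions are in the text and need correcting before the first comparative analysis at the 18-month interim. After that, choosing the window would be a decision made with data in hand.

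For the start rule, the effect is negligible for FVIII users (0 to 6 days) and material only for emicizumab users: nominally 54 weeks, and about 22 to 53 weeks if emicizumab ends 0 to 26 weeks after infusion. That range rests on the assumed end dates and on whether the 5-week floor applies. The cohort-level effect cannot be computed, because the share of Roctavian participants coming from emicizumab is not given.

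For the baseline window, either reading of Table 8 lets a score up to 91 days after infusion serve as baseline. The printed reading also excludes scores the protocol asked for on days -60 to -1. The size of the resulting bias cannot be derived from the documents.

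**What to change.** 1. Make the wording of SAP 7.3.3.2 identical to SAP 7.2.3 and protocol 10.3.2.3.
2. In SAP Table 8, set the baseline window to day -60 through index, before infusion in the Roctavian Cohort, taking the score closest to index. Exempt the baseline row from the two-sided footnote. Leave the 6-month window starting at day 92; scores from days 1 to 91 may be listed but never used as baseline.

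The cost is two wording corrections, with no change to sample size or data collection. The downside is that participants whose first score falls after index have no baseline for the change analyses; their number is unknown and should be reported by cohort.
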